## scenario summary

project name	A lung ultrasound-guided strategy for preventing ventilator-associated pneumonia in newborns
purpose of research	This prospective randomized controlled trial, conducted from December 2023 to December 2025, enrolled full-term newborns requiring continuous mechanical ventilation for over 48 hours. The study evaluated whether a lung ultrasound-guided position adjustment strategy could reduce the risk of ventilator-associated pneumonia (VAP) in these infants compared to the traditional empirical position adjustment protocol.
research design	Eligible infants were randomly assigned in a 1:1 ratio to receive either conventional positioning management or LUS-guided positioning management. The LUS-guided group underwent bedside ultrasound assessments twice daily to monitor for atelectasis or consolidation, with positional adjustments made based on findings to optimize dependent drainage and ventilation-perfusion coupling. Primary endpoints included VAP incidence, while secondary endpoints comprised mechanical ventilation duration, feeding intolerance, pulmonary hemorrhage, pneumothorax, new intracranial hemorrhage, mortality, and ICU length of stay.
Total study cases	94 cases (47 cases per group)
Case Selection	Inclusion criteria: Full-term newborns (gestational age 37-42 weeks) requiring continuous mechanical ventilation for over 48 hours. The diagnosis of VAP follows the guidelines established by the U.S. Centers for Disease Control and Prevention (CDC) (18), applicable to infants under one year old receiving mechanical ventilation for more than 48 hours. Diagnosis requires: chest imaging demonstrating new or progressively worsening pulmonary infiltrates, accompanied by deterioration in gas exchange function.

	
Additionally, at least three of the following clinical or laboratory findings must be present: abnormal body temperature (rectal temperature <math>>38^{\circ}\text{C}</math> or <math><35.5^{\circ}\text{C}</math>), leukopenia (WBC <math><4 \times 10^9 /L</math>) or leukocytosis (WBC <math>>15 \times 10^9 /L</math>) with left shift (<math>>10\%</math> band cells), purulent or increased tracheal secretions, altered sputum characteristics, increased secretions requiring frequent suction, apnea, signs of respiratory distress (tachypnea, chest retractions, wheezing, nasal flaring), abnormal breath sounds, bradycardia (<math><100</math> bpm) or tachycardia (<math>>170</math> bpm).

--	--

	
Exclusion criteria: ① Premature infants; ② Neonates with early-onset sepsis or prior pneumonia; ③ Patients unsuitable for enteral nutrition; ④ Neonates requiring mechanical ventilation for surgical procedures; ⑤ Infants with multiple congenital anomalies or suspected chromosomal abnormalities. Any of these criteria must be met for exclusion from the study.

therapeutic regimen	
All infants underwent invasive ventilation via endotracheal intubation using the SLE6000 mechanical ventilator with a heated humidification system, employing disposable respiratory circuits. Both groups received standard NICU care including standardized VAP prophylaxis, antibiotic therapy when indicated, and routine nursing management in accordance with hospital policies and international guidelines. Antibiotic selection and adjustment followed local antimicrobial stewardship guidelines, with modifications based on culture and susceptibility results. The control group received conventional positioning management, while the LUS-guided group utilized lung ultrasound-guided positioning management.

Efficacy Evaluation	
Effectiveness evaluation indicators (main efficacy indicators and secondary efficacy indicators)
 
Main therapeutic index: the effect of lung ultrasound-guided positioning management on the incidence of ventilator-associated pneumonia in newborns with mechanical ventilation.
 
Secondary efficacy endpoints included feeding intolerance in newborns, pulmonary hemorrhage, pneumothorax, new-onset intracranial hemorrhage, mortality, duration of invasive mechanical ventilation (from initiation to successful extubation or death), and NICU length of stay.
 
Safety evaluation indicators: mortality and complication incidence

----------------------------	---

Statistical Methods	
Statistical analysis was performed using IBM SPSS Statistics (version 20.0; IBM Corporation, Amherst, New York, USA). Continuous variables were presented as mean <math>\pm</math> standard deviation (SD) or median (interquartile range, IQR) based on their distribution patterns, while categorical data were expressed as frequencies and percentages. Categorical variables were compared using chi-square test or Fishers exact test, whereas continuous variables were analyzed using independent samples t-test or Mann-Whitney U test as appropriate. A two-tailed P-value <math><0.05</math> was considered statistically significant. This analysis strictly followed the original research protocol, with all procedures conducted as planned.

Study duration	From November 1, 2023 to December 31, 2025

## I. Research Background

Ventilator-associated pneumonia (VAP) ranks among the most prevalent and severe nosocomial infections in neonatal intensive care units (NICU), leading to prolonged mechanical ventilation, extended hospital stays, and increased mortality. The incidence of neonatal VAP (Neo-VAP) varies significantly across different monitoring criteria and patient populations: in high-income countries, it ranges from 1.4 to 7 cases per 1,000 ventilator days, while in developing countries, the figure can reach up to 89 cases per 1,000 ventilator days.  .

Premature infants and extremely low birth weight infants are exposed to invasive ventilation due to immature immune defense, impaired mucosal ciliary clearance function, and prolonged exposure to invasive ventilation  , which is high risk.

The pathogenesis of novel VAP involves three key mechanisms: microaspiration of contaminated secretions, colonization of biofilm on tracheal intubation, and gravity-dependent accumulation of airway secretions.  Inappropriate or static postures may exacerbate lung collapse and secretions retention, leading to ventilation-perfusion mismatch, hypoxemia, and bacterial overgrowth. Studies in adult and pediatric patients demonstrate that appropriate positioning interventions—such as semi-recumbent or prone positions—can improve oxygenation and potentially reduce VAP incidence.  However, these strategies have not been sufficiently standardized or validated in newborns, as their immature thermoregulation and unstable hemodynamics limit frequent positional adjustments.  .

Lung ultrasound (LUS) has emerged as a reliable, radiation-free bedside imaging tool for dynamic assessment of pulmonary ventilation, atelectasis, and consolidation in newborns.  The quantitative LUS score provides real-time assessment of regional ventilation, enabling early detection of asymmetric ventilation patterns.  By incorporating LUS findings into positional management, we can develop physiologically based strategies to optimize lung re-expansion and secretions clearance before irreversible infection occurs.

However, clinical evidence supporting this approach in newborns remains limited. To address this, our study evaluated the clinical effectiveness of lung ultrasound-guided targeted interventions in preventing mechanical ventilation-associated pneumonia (Neo-VAP). We hypothesized that LUS-guided personalized interventions would reduce VAP incidence and improve respiratory function compared to conventional care-guided positioning.

## **II. Research Objectives**

[figure not shown]
- 1. The primary objective was to evaluate whether a lung ultrasound-guided positioning strategy could reduce the risk of ventilator-associated pneumonia (VAP) in mechanically ventilated newborns compared to traditional empirical positioning protocols.**
- 2. Secondary objective: To enhance the effectiveness of VAP prevention in newborns and expand the clinical applications of ultrasound technology.**

## **III. Types of research design, principles and experimental steps**

### **1. research design**

This prospective randomized controlled trial was conducted from December 2023 to December 2025 at the Tertiary ICU of Guangdong Second Peoples Hospital, enrolling full-term newborns requiring continuous mechanical ventilation for over 48 hours. Eligible infants were randomly assigned in a 1:1 ratio to receive either conventional position management or LUS-guided position management. The LUS-guided group underwent bedside ultrasound assessments twice daily to monitor atelectasis or consolidation, with position adjustments made based on evaluation results to optimize dependent drainage and ventilation-perfusion matching. Primary outcome was VAP incidence, while secondary outcomes included mechanical ventilation duration, feeding intolerance, pulmonary hemorrhage, pneumothorax, new intracranial hemorrhage, mortality, and ICU length of stay.

### **2. stages of research**

## IV. Case Selection

This prospective randomized controlled trial was conducted from December 2023 to December 2025 at the tertiary ICU of Guangdong Second Peoples Hospital, enrolling full-term newborns requiring continuous mechanical ventilation for over 48 hours.

### 1. Selection criteria

All enrolled newborns underwent prospective observation to monitor the incidence of ventilator-associated pneumonia (VAP). VAP diagnosis was based on the criteria established by the U.S. Centers for Disease Control and Prevention (CDC).

 This is indicated for infants under one year of age receiving mechanical ventilation for more than 48 hours. Diagnosis requires: chest imaging demonstrating new or progressive pulmonary infiltrates with deterioration of gas exchange function.

Additionally, at least three of the following clinical or laboratory findings must be present: abnormal body temperature (rectal temperature  $>38^{\circ}\text{C}$  or  $<35.5^{\circ}\text{C}$ ), leukopenia (WBC  $<4\times10^9/\text{L}$ ) or leukocytosis (WBC  $>15\times10^9/\text{L}$ ) with left shift ( $>10\%$  band cells), purulent or increased tracheal secretions, altered sputum characteristics, increased secretions requiring frequent suction, apnea, signs of respiratory distress (tachypnea, chest retractions, wheezing, nasal flaring), abnormal breath sounds (rheumus, crackles, or snoring), bradycardia ( $<100$  bpm) or tachycardia ( $>170$  bpm).

## **2. Exclusion criteria**

- ① premature ;
- ② Neonates with early sepsis or previous pneumonia;
- ③ Not suitable for patients with enteral nutrition;
- ④ Newborns requiring mechanical ventilation due to surgery;
- ⑤ There are many infants with congenital abnormalities or suspected chromosomal abnormalities.

Those who meet any of the above criteria will be excluded and excluded from this study.

## **3. Filter criteria**

Participants enrolled in the group who meet one of the following criteria should be excluded:

- (1) Those who do not meet the inclusion criteria or meet the exclusion criteria after inclusion.
- (2) No record.
- (3) Individuals who have not used the trial drug or intervention.

The analysis set is determined by a blind review meeting to exclude cases. The reasons for exclusion should be documented, and the original data should be retained for reference.

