### **Control group (standard positioning management)**

Infants in the control group had their positions adjusted every two hours, alternating between supine, left lateral, right lateral, and prone positions.  The head of the bed should be elevated 15°-30° with the body in a slightly flexed position—hips aligned along the midline, shoulders slightly forward, head centered, and arms

free to move. Position adjustments should only be made when vital signs are stable and resuscitation is delayed, or when adjusting the ventilator, administering IV fluids, or managing deep sleep. If heart rate fluctuates more than 20 beats per minute or SpO2 drops below 90% (excluding airway obstruction), the interval between position adjustments should be extended to 3-4 hours. This group did not undergo ultrasound evaluation.

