## VII. Criteria for efficacy evaluation

Main efficacy criteria: the effect of lung ultrasound-guided positioning management on the incidence of ventilator-associated pneumonia in mechanical ventilation newborns.

Secondary efficacy criteria included feeding intolerance in newborns, pulmonary hemorrhage, pneumothorax, new intracranial hemorrhage, mortality, duration of invasive mechanical ventilation (from initiation to successful extubation or death), and NICU hospitalization duration.

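### Filter rule (1) can drop randomised infants for conditions that arise after allocation, including unsuitability for enteral nutrition, which overlaps the secondary endpoint feeding intolerance

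*Protocol*

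**What the plan says.** Protocol section IV, 3. Filter criteria, opens: "Participants enrolled in the group who meet one of the following criteria should be excluded". It therefore concerns infants who already have an allocation. Its first rule covers "Those who do not meet the inclusion criteria or meet the exclusion criteria after inclusion". The same section makes this an analysis-set rule: "The analysis set is determined by a blind review meeting to exclude cases". Reasons must be documented and the original data kept. The Protocol names no analysis set that retains every randomised infant.

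Two entries in 2. Exclusion criteria matter here. Criterion 3 reads "Not suitable for patients with enteral nutrition"; the scenario summary shows that this means infants unsuitable for enteral nutrition. Neither version states when it is assessed. Criterion 2 reads "Neonates with early sepsis or previous pneumonia", and in the summary "Neonates with early-onset sepsis or prior pneumonia". Neither says what the pneumonia must precede: birth, intubation, the 48-hour point or randomisation.

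Section VII states: "Secondary efficacy criteria included feeding intolerance in newborns, pulmonary hemorrhage, pneumothorax, new intracranial hemorrhage, mortality". The primary endpoint is VAP incidence. The ultrasound arm is scanned at 08:00 and 18:00 every day. Of the control arm the Protocol says: "This group did not undergo ultrasound evaluation".

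**The concern.** Eligibility criteria are normally applied once, before allocation. Here they continue to act on randomised infants and decide who is analysed. When a criterion can be met through a condition that is also counted as an outcome, following the rule removes outcome events. The rates that remain describe a group selected on what happened after randomisation, and the balance that randomisation provides is no longer assured.

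Criterion 3 creates this overlap directly. An infant whose feeding intolerance becomes severe enough to rule out enteral nutrition has a secondary-endpoint event and also meets an exclusion criterion after inclusion. Because the whole infant is removed, the primary outcome, mortality and ventilation time go too.

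Criterion 2 is a lesser problem. With no reference time, someone must decide after allocation whether an early consolidation is earlier pneumonia (infant removed) or VAP (infant counted as an event).

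**Working it through.** **The plan's own figure.** The scenario summary gives 47 + 47 = 94 infants. It states no VAP rate, feeding-intolerance rate, power or dropout, so there is no effect size to reproduce. Every rate and count below is assumed.

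**Step 1: which criteria can be met after allocation?**

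- Criterion 1 (prematurity) and criterion 5 (congenital or chromosomal abnormality) are fixed at birth. They can be discovered late but cannot arise late.
- Criterion 2 carries time words (early sepsis, earlier pneumonia) but no reference point for the pneumonia.
- Criterion 3 (enteral nutrition) has no time word and can arise at any point during ventilation.
- Criterion 4 concerns the reason for ventilation. An infant ventilated for another reason who later needs an operation does not plainly meet it.

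Only criterion 3 can plainly arise after allocation and overlap an endpoint.

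**Step 2: effect of removing events in one arm.** If a fraction f of infants with an event of risk p is removed, the apparent risk is

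p(1 − f) / (1 − pf).

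Assume 8 feeding-intolerance cases among 47 infants, with 3 filtered out: p = 8/47 = 17.0% and f = 3/8. The apparent risk is (5/47)/(44/47) = 5/44 = 11.4%, a fall of 5.6 or 5.7 points (17.02 − 11.36 = 5.66) with no change in the infants' condition.

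**Step 3: the same fraction lost in both arms.** The formula holds for any yes/no outcome whose events are removed. With f = 25% and 47 per arm before removal:

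| Assumed true risks | Apparent risks | Difference (points) | Power |
|---|---|---|---|
| 40% v 15% | 33.3% v 11.7% | 25 to 21.6 | 78% to 69% |
| 30% v 10% | 24.3% v 7.7% | 20 to 16.6 | 68% to 58% |

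A review blind to arm would still allow this loss, because it requires no knowledge of allocation.

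**Step 4: events lost in the ultrasound arm only, no true effect.** Exact enumeration of the two-sided 5% chi-square test without continuity correction, equal true risks of 20% to 40%, 47 per arm:

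| f | Infants removed on average | Type I error |
|---|---|---|
| 0 | 0 | 4.8% to 5.1% |
| 10% | 0.9 to 1.9 | 5.6% to 5.9% |
| 25% | 2.4 to 4.7 | 8.2% to 10.1% |
| 50% | 4.7 to 9.4 | 21% to 31% |

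For VAP, Steps 3 and 4 apply only if the review meeting reads the pneumonia criterion to include pneumonia found after enrolment. They show how sensitive a trial of this size is to a few removals; they do not predict what will happen.

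**The case against.** The best defence is that rule (1) is meant for ineligibility recognised late: the clause on exclusion criteria sits beside one on unmet inclusion criteria, and together they read naturally as a clean-up of enrolment errors. The meeting is blind, reasons are recorded and data are kept, so a full analysis remains possible. A fuller definition of analysis sets may also stand in an SAP that is not at hand. Unsuitability for enteral nutrition is not the same as feeding intolerance, and only one of several secondary endpoints is touched directly.

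Much of this is fair, but the intended reading is not what the rule says. Nothing confines it to conditions present before randomisation, and criterion 3 does not supply the limit. Overlap short of identity is enough to lose events. Blinding and record-keeping make the loss visible without restoring it.

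Three stronger inferences are tempting and should not be drawn:

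- *That the rule removes VAP cases.* Both versions of criterion 2 refer to earlier pneumonia, so pneumonia arising after enrolment is not plainly covered.
- *That more infants will be filtered from the ultrasound arm because it is scanned.* No section makes study ultrasound a source for eligibility; it guides positioning. Section VI gives chest radiographs on ventilation days 1, 3 and 7 without distinction by arm. The VAP definition also requires an infiltrate that is new or worsening, so a consolidation judged to be old would not by itself count as VAP. What stands is that only one arm has the extra imaging that could inform the judgement. The asymmetry is possible, not demonstrated.
- *That later surgery triggers criterion 4.* Its wording concerns why the infant is ventilated, and intestinal perforation is handled separately under 5. Termination criteria.

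**Conclusion.** The concern holds for the analysis-set rule and for criterion 3. As written, rule (1) allows randomised infants to be removed for a condition that arises after allocation and overlaps feeding intolerance, and all their other outcomes leave with them. For the primary endpoint the defect is narrower: an undefined reference time leaves a classification to judgement after allocation, with more imaging available in one arm.

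The size cannot be determined from the Protocol. On the assumed counts, three removals shift a feeding-intolerance rate by about 5.7 points. With no true effect and a quarter of events lost in one arm only, the test's error rate rises from about 5% to between 8.2% and 10.1%; at a 10% loss it stays below 6%. These figures depend on the assumed risks and on the removed infants being event cases.

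**What to change.** 1. Reword the whole of rule (1), not just its second half. Eligibility should be judged only on conditions present before randomisation, using information available equally in both arms. Deleting only the clause on exclusion criteria would leave the clause on inclusion criteria still removing randomised infants.
2. State the time point against which earlier pneumonia in criterion 2 is judged.
3. Make the primary analysis include all randomised infants in their allocated arm. Record conditions that arise or are found after randomisation as outcomes or protocol deviations.
4. Report any filtered analysis as a sensitivity analysis, with the number of infants removed by arm and reason.

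The cost is a short amendment. A few infants who prove ineligible in hindsight stay in, which slightly dilutes the contrast. If recruitment has ended, items 3 and 4 can still be adopted, since the filter criteria require original data to be retained.

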#### LUS Guided Group (Lung Ultrasound Guided Localization)

Postural adjustments follow three principles: ensuring effective drainage of the affected lung area, optimizing ventilation of the healthy area, and preventing stress-related injury  In addition to routine care, two LUS assessments are conducted at fixed times daily (08:00 and 18:00) to guide individualized position adjustments by monitoring regional ventilation.

- If unilateral atelectasis or pulmonary edema is detected, the patient should first be maintained in dependent lateral position for approximately 1 hour, then transition to the contralateral or prone position for 3 hours.
- For lesions previously managed by the department, the prone position duration is reduced to 1 hour, while supine or lateral positions are extended to 3 hours.
- For posterior lesions, the supine or lateral position should be limited to 1 hour, while the prone position should be extended to 3 hours.
- Resume the standard two-hour shift system once the symptoms or edema have subsided.

If SpO2 remains persistently below 90% (excluding operational or feeding disturbances), the respiratory rate increases by more than 20 breaths per minute from baseline, or airway secretions significantly increase, an additional LUS evaluation is required.

All ultrasound examinations are performed by two pediatricians with professional training, while the imaging data undergoes quality review by senior neonatologists with pulmonary ultrasound experience. All physicians receive semi-annual intensive care ultrasound hands-on training from internationally certified instructors to ensure consistent diagnostic standards and standardized technical procedures.

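### The filter rule drops enrolled infants for post-randomisation reasons, including treatment received, and the protocol never analyses all randomised infants as assigned

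*Protocol*

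**What the plan says.** Section IV.3 applies to infants already in the trial: "Participants enrolled in the group who meet one of the following criteria should be excluded". It lists three grounds:

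1. Eligibility: "Those who do not meet the inclusion criteria or meet the exclusion criteria after inclusion".
2. Having no record.
3. Treatment received: "Individuals who have not used the trial drug or intervention".

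The section then adds: "The analysis set is determined by a blind review meeting to exclude cases". It also requires that "The reasons for exclusion should be documented, and the original data should be retained for reference".

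Section X (Statistical processing) and the statistical part of the summary name tests and a two-sided 0.05 level, but no analysis population. Sections IV.4 and IV.5 set out withdrawal and termination rules without saying whether those infants stay in the analysis. Nowhere does the protocol say that all randomised infants are analysed in the arm to which they were assigned.

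**The concern.** Randomisation makes the two arms comparable at the moment of allocation. A rule that later removes infants because of what happened to them can undo that, especially if it works differently in the two arms.

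- **Ground 3** selects on treatment received. The trial has no drug, and the rule does not say what using the intervention means for a control infant, who gets scheduled turning and of whose group the protocol says "This group did not undergo ultrasound evaluation". In practice the rule falls mainly on the LUS arm.
- **Ground 1** is not limited to facts that existed before randomisation. One exclusion criterion, "Not suitable for patients with enteral nutrition", can arise during follow-up and lies close to the secondary outcome of feeding intolerance. If infants are randomised before 48 hours of ventilation (the timing is not stated), early extubation could also lead to removal.
- **Ground 2** turns missing data into exclusions, so they drop out of the comparison instead of being counted as missing.

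At stake is the population for the primary endpoint. This is not a detail left to a statistical analysis plan. The protocol itself fixes the rule, and a later plan with an as-randomised primary set would contradict it.

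**Working it through.** **Inputs from the protocol:** 47 infants per arm (summary); VAP incidence as primary outcome (section III.1); chi-square or Fisher's exact test at two-sided 0.05 (section X); scans at 08:00 and 18:00 (section VI, LUS group). **Not given:** VAP rate, number removed, and VAP risk in removed infants. Those values are assumed below. The protocol has no figure of its own on this point to reproduce.

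**Reach of ground 3.** The protocol says "two LUS assessments are conducted at fixed times daily (08:00 and 18:00". The longest gap between scheduled scans is from 18:00 to 08:00, which is 14 hours. Few LUS infants should go entirely without a scan, so small numbers removed are the more plausible.

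**Apparent relative risk with no true effect.** Let *n* of 47 LUS infants be removed, with VAP risk *k* times the average *p*. The retained LUS risk is *p*(47 − *kn*)/(47 − *n*). The control risk is *p*, so

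RR = (47 − *kn*)/(47 − *n*),

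which does not depend on *p* (for *k* = 2, *p* can be at most 50%).

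| Removed from LUS arm | *k* = 2 | *k* = 0 |
|---|---|---|
| 1 | 45/46 = 0.978 | 47/46 = 1.022 |
| 3 | 41/44 = 0.932 | 47/44 = 1.068 |
| 5 | 37/42 = 0.881 | 47/42 = 1.119 |
| 7 | 33/40 = 0.825 | 47/40 = 1.175 |

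If 5 LUS infants and 2 controls are removed, the RR is (37/42)/(43/45) = 0.922 for *k* = 2 and 45/42 = 1.071 for *k* = 0. Equal removals at equal risk give 1.00.

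**Type I error.** Exact binomial enumeration, 30% VAP in both arms, removals from the LUS arm only, *k* = 2:

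| Removed | Retained LUS risk | Uncorrected chi-square | Fisher |
|---|---|---|---|
| 0 | 0.300 | 5.1% | 3.1% |
| 1 | 0.293 | 5.0% | 3.9% |
| 2 | 0.287 | 5.3% | 4.0% |
| 3 | 0.280 | 5.8% | 4.6% |
| 5 | 0.264 | 6.6% | 5.0% |
| 7 | 0.248 | 8.1% | 6.5% |

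**A borderline result.** Suppose 14/47 controls and 7/47 LUS infants have VAP, and LUS infants with VAP are then removed:

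| LUS arm | Chi-square p | Fisher p |
|---|---|---|
| 7/47 | 0.083 | 0.136 |
| 6/46 (one removed) | 0.049 | 0.076 |
| 5/45 (two removed) | 0.027 | 0.039 |

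One removal crosses 0.05 under chi-square; it takes two under Fisher.

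**The case against.** The best defence is that the rule will touch few infants and is reviewed blind. Ground 3 concerns infants who never received the intervention, not partial adherence, and the scan schedule makes that rare. The mention of a drug suggests template text. Ground 1 reads naturally as ineligibility at entry that is discovered late, an exclusion most statisticians would accept. An infant with no record cannot supply an observed outcome under any analysis. With 1 to 3 removals the chi-square error stays between 5.0% and 5.8%, and the borderline example was chosen near the threshold and removes infants certain to have VAP.

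Much of this stands as a limit on size. The likely effect is modest, and the larger removal counts are illustrations. It does not rescue the rule:

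- The wording of ground 1 is not confined to pre-randomisation facts, and grounds 1 and 2 are not bounded by the 14-hour gap.
- Blind review restrains outcome-driven choices, but a blinded meeting that applies a treatment-received rule still produces a treatment-received set. For ground 3, the absence of a LUS scan as the stated reason also reveals the arm.
- An infant without an outcome still belongs in the randomised count and should be reported by arm.

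It is also fair to say that withdrawals under sections IV.4 and IV.5 may be a larger source of loss. An as-randomised primary set would cover those infants too.

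**Conclusion.** The concern holds, and the rule is wrong as written: the set for the VAP comparison can depend on events after randomisation and can differ by arm. Neither the direction nor the size of the bias can be determined from the protocol. Under the assumptions shown (no true effect, LUS-only removals at double or zero risk), the distortion of the relative risk is about 2% with one infant removed and about 12% with five. The effect on type I error is negligible for one or two removals and grows after that. If removals are balanced between the arms and carry equal risk, the relative risk is not distorted. It must be corrected because it defines the primary analysis population, not because a large bias has been shown. The retained original data keep an as-randomised analysis possible wherever records exist, but the protocol does not call for one.

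**What to change.** Replace section IV.3 with wording such as:

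> The primary analysis includes every randomised infant in the assigned arm, whatever positioning was received and whether or not the infant later left the trial procedures. An infant may be removed only for ineligibility shown from data recorded before randomisation, judged by someone unaware of arm and outcome. Randomised infants with no outcome record are missing data, not exclusions. They are reported by arm, and a sensitivity analysis counts them as VAP in one arm and no VAP in the other, then the reverse. The set obtained by applying the three filter criteria is a labelled per-protocol sensitivity analysis, with exclusions and reasons reported by arm.

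Also state when randomisation takes place relative to 48 hours of ventilation.

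The cost is one paragraph, one sentence on timing and two short sensitivity analyses. The one drawback is that infants who did not receive LUS guidance may slightly dilute the estimated effect.
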